### 3.2.2 Adverse Events

For adverse events with incomplete dates, the following rules will be used to impute start and/or stop dates for the sole purpose of determining if an AE is treatment-emergent in the MTX Run-in Period or Pegloticase + MTX Period. Imputed dates will not appear in the data listings.

For partial start dates:

- If the month and year of adverse event onset/worsening are provided but day is missing
  - If the month and year match the month and year of the first dose of MTX in the MTX Run-in Period AND match the month and year of the first infusion of pegloticase in the Pegloticase + MTX Period, the first dose date of MTX in the Run-in Period will be imputed and the event will be considered treatment emergent in the MTX Run-in Period and Pegloticase + MTX Period.
  - Otherwise, if the month and year match the month and the year of the first dose date of pegloticase, the day of the first infusion date of pegloticase will be imputed and the AE will be considered treatment-emergent in the Pegloticase + MTX Period.
  - Otherwise, if the month and year match the month and the year of the first dose date of MTX, the day of the first dose date of MTX will be imputed and the AE will be considered treatment-emergent in the MTX Run-in Period.

- Otherwise, the first of the month will be used and the treatment-emergent status will be assessed relative to the first infusion date of pegloticase and the first dose date of MTX.
- If the year of adverse event onset is provided, but the month and day are missing
  - If the year matches the year of the first dose of MTX in the MTX Run-in Period AND matches the year of the first infusion of pegloticase in the Pegloticase + MTX Period, the first dose date of MTX in the Run-in Period will be imputed and the event will be considered treatment emergent in the MTX Run-in Period and Pegloticase + MTX Period.
  - Otherwise, If the year matches the year of the first infusion date of pegloticase, the month and the day of the first infusion date of pegloticase will be imputed, and the AE will be considered treatment-emergent in the Pegloticase + MTX Period.
  - Otherwise, if the year matches the year of the first dose date of MTX, the month and day of the first dose of MTX will be imputed and the AE will be considered treatment-emergent in the MTX Run-in Period.
  - Otherwise, January 1st will be used and the treatment-emergent status will be assessed relative to the dosing start date of pegloticase and the first dose date of MTX.
- If the start date is completely missing, the AE will be considered treatment-emergent in the Pegloticase + MTX Period and the MTX Run-in Period, unless the stop date is complete or provides enough partial information to rule out a treatment-emergent status in the Treatment Period. This should be a rare occurrence.
- If the stop date is complete and the imputed start date is after the actual stop date, then the start date will be imputed as the stop date.

Events with missing relationship to study drug in the MTX Run-in period will be considered “related” to Methotrexate for statistical summaries. Events with missing relationship to study drug in the Pegloticase + MTX period will be considered “related” to Methotrexate and “related” to pegloticase for statistical summaries.

Missing severities will be considered “severe” for statistical summaries. Any preferred terms with a missing severity will be described in the table footnotes.

### **3.3 Study Subjects**

#### **3.3.1 Subject Disposition**

Subject disposition corresponding to the MTX Run-in Period will be summarized for all subjects combined. Subject disposition corresponding to the Pegloticase + MTX Period will be summarized by assigned infusion duration group and overall.

For disposition summaries corresponding to the MTX Run-in Period, the denominator for percentages corresponding to the subjects who discontinued or completed the MTX Run-in Period and to subjects who entered the Pegloticase + MTX Period will be based on the number of subjects who entered in the MTX Run-in Period. The denominator for all other percentages in the MTX Run-in Period will be based on the number of subjects who were screened.

Disposition for the MTX Run-in Period will include the number and percentage of subjects who:

- Screened
- Overall Screen Failures, with reason (unable to tolerate MTX vs. other)
- Entered the MTX Run-in Period (ITT Set)
- Discontinued from the MTX Run-in Period (MTX screen failure)
- Completed the MTX Run-in Period
- Entered the Pegloticase + MTX Period

For summaries corresponding to the Pegloticase + MTX Period, the number of subjects entering the Pegloticase + MTX Period (mITT analysis set) will be used for the denominator of the percentages. Disposition summaries for the Pegloticase + MTX Period will include the number and percentage of subjects who:

- Are in the mITT, Safety, and the PK analysis sets
- Completed treatment in the Pegloticase + MTX Period
- Discontinued early from treatment in Pegloticase + MTX Period along with reason for discontinuation
- Discontinued early from treatment in the Pegloticase + MTX Period but continued in the study
- Completed the study
- Discontinued early from the study along with reason for early discontinuation

A shift table will also be created to demonstrate any shift subjects had from the original assigned infusion duration to other infusion durations. Shifts will be presented for the last visit in the Pegloticase + MTX Period and by each visit. Denominator for overall shift percentage will be the total number of subjects assigned to each treatment group at Day 1 visit. Denominator for the per-visit shift percentage will be the total number of subjects assigned to each treatment group at Day 1 visit who also attended the indicated visit.

### 3.3.2 Study Visits

A summary of the number and percentage of subjects attending each visit by treatment period will be provided. The denominator for the MTX Run-in Period will be the number of subjects in

the ITT analysis set; the denominator for the Pegloticase + MTX Period will be the number of subjects in each assigned treatment group in the mITT (equivalently, Safety) analysis set.

### 3.3.3 Protocol Deviations

All protocol deviations and the reasons for such deviations will be documented in the eCRF. Sites will be issued specific instructions to follow in order to capture missed visits, out of window visits, treatment interruptions and treatment discontinuations due to COVID-19 on the eCRF. Details to be recorded include whether a subject has suspected or confirmed COVID-19 infection and whether the study site is open or closed. Deviations will be categorized by type and as major or minor. In the event of a major protocol deviation, the Investigator and Sponsor's Medical Monitor will determine whether the subject should continue to participate in the study.

All protocol deviations will be provided for the ITT analysis set as a summary by period of occurrence, and by type and in total. Protocol deviations in the screening period and MTX Run-in Period will be summarized for the MTX treatment group. Protocol deviations from the pegloticase + MTX treatment period will be summarized by assigned infusion duration group.

A single listing of all protocol deviations will also be created, including period of occurrence (screening, MTX Run-in, Pegloticase + MTX Period, and Follow-up Period).

### 3.3.4 Demographic and Baseline Characteristics

Demographic data, including age (years), age category (< 65 years,  $\geq$  65 years), race, childbearing potential, ethnicity and sex, height (cm), weight (kg) will be summarized for the ITT and mITT analysis sets.

Baseline characteristics, including time since first gout attack and diagnosis (in years), presence of uric acid crystals confirming diagnosis, number of (acute) flares in past 12, 6, and 1 month(s), pattern of flares, typical severity of flares, chronic gout synovitis/arthropathy status, prior/current tophi, history of overnight hospital stay for gout, history of surgery for gout (excluding arthrocentesis), history of kidney stones, episodes of renal colic (past year), kidney function impact by gout, and urate lowering therapy will be summarized for the ITT and mITT analysis sets using descriptive statistics.

Summaries of demographic and baseline characteristics for the mITT analysis set will be by assigned infusion duration and overall. Listings will include all screened subjects.

Results collected at the screening visit will be used for analysis.

### 3.3.5 Medical History

Medical history, including surgical history and symptom severity, will be conducted at the screening visit and summarized for the ITT and mITT analysis sets. Medical history events will be summarized overall and by SOC and PT in alphabetical order.

The coding of an AE, medical history and concomitant medication terms will be performed by EMB Statistical Solutions and reviewed and approved by a Horizon Therapeutics Medical Monitor.

### 3.3.6 Prior and Concomitant Medications and Procedures

Prior medications will include any medications, with a start date prior to (but not including) the start date of MTX dosing. Prior medications (not including gout medications) will be collected for 1 year prior to screening.

Concomitant medications include drug or biological products other than the study drugs (or prior gout medications) taken by a subject after a dose of study drug. This includes other prescription medications (including preventive vaccines), over the counter medications, herbal medications, vitamins and food supplements.

Prior medications, concomitant medications used during the MTX Run-in Period, and concomitant medication used in the Pegloticase + MTX Period will be summarized by presenting the counts and percentage of subjects using medications overall for the ITT and Safety Analysis Sets as appropriate. Summaries will be presented by Anatomical Therapeutic Chemical (ATC) Level 4 term and preferred drug name. Medication summaries will be sorted alphabetically by ATC Level 4 and by preferred drug name within ATC Level 4 for the ITT and Safety Analysis Sets. Subjects will be counted only once for each medication class and each preferred drug name.

Concomitant medications used during the Pegloticase + MTX Period will be summarized by “as-assigned” infusion duration group for the safety analysis set.

Concomitant medications will be coded using the World Health Organization Drug (WHO Drug) Global B3 March 2020 dictionary.

Prior medications, concomitant medications, and medications during the Follow-up Period will be listed together with a designation to identify the period(s) of usage and sorted by start date. The listing will also include the infusion duration that corresponds to the start of the concomitant medication (as described in Treatment Windowing for “As-Treated” Summaries ([Section 3.1.6](#))). For determination of period(s) of use, missing date imputation rules are provided in Medication Dates ([Section 3.2.1](#)).

For medications with completely missing dates, the following rules will be used to assign prior, concomitant, and follow-up (concomitant medications used > 30 days after the last dose of Pegloticase or MTX in the Pegloticase + MTX Period):

Medication Start Date	Medication End Date	Prior	Concomitant in MTX Run-in Period	Concomitant in Pegloticase + MTX Period	Follow-up (> 30 days after last dose of Pegloticase or MTX in the Pegloticase + MTX Period)
Unknown	Unknown	Yes	Yes	Yes	Yes
Unknown	< first dose of MTX	Yes	No	No	No
Unknown	≥ first dose of MTX and < first dose of Pegloticase	Yes	Yes	No	No
Unknown	≥ first dose of Pegloticase and ≤ 30 days after last	Yes	Yes	Yes	No

Medication Start Date	Medication End Date	Prior	Concomitant in MTX Run-in Period	Concomitant in Pegloticase + MTX Period	Follow-up (> 30 days after last dose of Pegloticase or MTX in the Pegloticase + MTX Period)
	Pegloticase/MTX dose				
Unknown	≥ first dose of Pegloticase and > 30 days after last Pegloticase/MTX dose	Yes	Yes	Yes	Yes
< first dose of MTX	Unknown	Yes	Yes	Yes	Yes
≥ first dose of MTX and < first dose of pegloticase	Unknown	No	Yes	Yes	Yes
≥ first dose of pegloticase and ≤ 30 days after last pegloticase/MTX dose	Unknown	No	No	Yes	Yes
> 30 days after last pegloticase/MTX dose	Unknown	No	No	No	Yes

Any medication with a start date prior to the date of first dose of treatment in the MTX Run-in Period will be considered a prior medication.

The following medications will be considered concomitant in the MTX Run-in Period:

- A medication with a start date on or after the first dose date of MTX in the MTX Run-in Period but excluding medications with:
  - Start date on or after the first infusion date of pegloticase and
  - Start date more than 30 days after the last MTX dose, for subjects who did not receive an infusion of pegloticase.
- Medications with a partial start date with month and year of start provided and the year of start and month of start match the month and year of first MTX date and match the month and year of first pegloticase infusion will be classified as being used in the MTX Run-in Period and in the Pegloticase + MTX Period.
- A medication with a start date prior to the first dose date of MTX in the MTX Run-in Period with a stop date strictly after the first dose date of MTX in the MTX Run-in Period

- A medication with a start date prior to the first dose date of MTX in the MTX Run-in Period that was ongoing.

The following medications will be considered concomitant in the Pegloticase + MTX Period:

- A medication with a start date on or after the first infusion date of pegloticase but excluding medications with start date more than 30 days after the date of the end of the last pegloticase or MTX infusion.
- A medication with a start date prior to the first infusion date of pegloticase in the Pegloticase + MTX Period with a stop date strictly after the first infusion date of pegloticase in the Pegloticase + MTX Period.
- A medication with a start date prior to the first infusion date of pegloticase in the Pegloticase + MTX Period that was ongoing.
- Medications with a partial start date with month and year of start provided and the year of start and month of start match the month and year of first MTX date and match the month and year of first pegloticase infusion will be classified as being used in the MTX Run-in Period and in the Pegloticase + MTX Period.

The following medications will be considered in the Follow-up Period:

- Any medications with 1) a start date prior to 30 days after last dose of study medication (MTX or pegloticase) that continued use or had a stop date on or after 30 days after the last dose of study medication, or 2) a medication with a start date more than 30 days after the last dose of study medication

Concomitant procedures will be listed.

### 3.4 Endpoint Analysis

Potential intercurrent events (ICE) like discontinuing from the treatment may occur during the study. Subjects who discontinue from the treatment will be encouraged to stay in the study after and data will be collected through planned study completion. These intercurrent events will be addressed using different strategies in the efficacy and safety analyses as appropriate.

In general, treatment policy strategy will be used to account for the ICEs for defining estimands corresponding to continuous efficacy endpoints. For binary responder endpoints, composite strategy will be used. Safety endpoints will be assessed using a while-on-treatment strategy.

#### 3.4.1 Primary Endpoint Analysis

The primary analysis will be performed using the safety analysis set. The primary endpoint is the incidence of subjects experiencing IRs (including anaphylaxis) related to pegloticase from Day 1 to Week 24 in the cohort chosen to be the most desirable duration for infusion.

The estimand for the primary endpoint is defined by the following:

Population	Safety Analysis Set for the cohort chosen to be most desirable for infusion
Endpoint	Incidence of subjects experiencing IRs (including anaphylaxis) related to pegloticase
ICE	Early discontinuation of pegloticase
ICE Strategy	Only events that occur while the subject is receiving study pegloticase will be counted
Population-level Summary	Proportion of subjects who experience an IR (including anaphylaxis) related to pegloticase between Day 1 and Week 24

The primary analysis of the primary endpoint will be based on events adjudicated as IR (including anaphylaxis) by the adjudication committee. Adverse events adjudicated as IR will be considered to be related to pegloticase, regardless of the investigator causality assessment. The count and proportion of subjects with an IR (including anaphylaxis) related to pegloticase will be summarized, along with an a two-sided 95% exact (Clopper-Pearson) confidence interval for the proportion. The primary endpoint will be met if the upper bound of the 95% confidence interval is < 13%. Additionally, this endpoint will be analyzed for each of the other infusion duration cohorts. An additional summary based on reported events will be provided.

### 3.4.2 Secondary Endpoint Analyses

#### 3.4.2.1 Month 6 Responders

The estimand for the secondary endpoint for Month 6 responders is defined by the following:

Population	Modified Intent-to-Treat Analysis Set for the cohort chosen to be most desirable for infusion
Endpoint	Proportion of responders during Month 6
ICE	Early discontinuation of pegloticase; meeting sUA discontinuation criterion (sUA values > 6 mg/dL at 2 consecutive scheduled visits [excluding post-infusion sUA] starting at Week 2)
ICE Strategy	Participants who meet the sUA discontinuation criterion, or have < 2 sUA from separate visits available during Month 6 are considered treatment failures (non- responders). Available sUA results during Month 6 from participants who discontinue pegloticase for reasons other than meeting the sUA discontinuation criterion prior to Week 24 will be used in the response calculation.
Population-level Summary	Proportion of subjects who meet the response definition during Month 6

The proportion of responders during Month 6 will be summarized, along with a two-sided 95% exact (Clopper-Pearson) confidence interval for the proportion. A responder is defined as a subject for whom the proportion of time that the sUA-time curve is  $<6$  mg/dL during Month 6 (Weeks 20, 22 and 24) is at least 80%. The proportion of time that the sUA level is below 6 mg/dL is defined as the ratio of the time during which the sUA level remains below 6 mg/dL (using linear interpolation, if necessary) to the entire time interval during Month 6. Any unscheduled sUA collection during Month 6 will be included. Subjects with only one visit for sUA collection within the period will be considered non-responders, regardless of the value(s) of at the visit.

The number and proportion of subjects meeting the Individual Subject sUA Discontinuation Criteria will be summarized descriptively as part of the secondary endpoints.

A subject will be declared a non-responder if the subject had sUA level  $> 6$  mg/dL at 2 consecutive study visits beginning with the Week 2 Visit. In addition, a subject who withdraws from the study for any reason (other than meeting Individual Subject sUA Discontinuation Criteria) after the first dose of pegloticase in the pegloticase + MTX Period and prior to or during Month 6 will be considered a Month 6 non-responder if sUA values are not collected at the planned timepoints. The proportion of Month 6 responders by pegloticase baseline and post baseline ADA (positive /negative) status will be summarized similarly as the above. Please see Section 3.6.3.4 for the definition of pegloticase baseline and post baseline ADA status.

The proportion of time that the sUA level is below 6 mg/dL during Month 6 is defined as the ratio of the time during which the sUA level remains below 6 mg/dL (using linear interpolation, if necessary) to the entire time interval during Month 6. Results from visits where an infusion was not performed (e.g. subject discontinued pegloticase but remained in study) will be used when available. The subject-specific proportion of time during the period during which the sUA was less than 6 mg/dL will be summarized using descriptive statistics. If a subject has  $\leq 1$  data point in the period, then the proportion of time will not be calculated.

The number and proportion of subjects that discontinued treatment due to the stopping rule will be summarized. In addition, the number and proportion of subjects missing all data in analysis period will be summarized.

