15. Subjects will take folic acid 1 mg orally every day beginning at Week -4 (the start of MTX) until prior to the End of Pegloticase Infusions Visit (if applicable) or the Week 24/End of Study/Early Termination. Prescriptions are to be filled at a local pharmacy, as needed.
16. IR prophylaxis: fexofenadine (180 mg orally) administered the day before each infusion; fexofenadine (180 mg orally) and acetaminophen (1000 mg orally) administered on the morning of each infusion; and methylprednisolone (125 mg IV) will be administered over an infusion duration between 10 – 30 minutes, immediately prior to each pegloticase infusion.
17. For all subjects, serum samples for pegloticase PK analysis will be collected approximately 15 minutes to 2 hours after the end of infusion on Day 1; prior to infusion and approximately 15 minutes to 2 hours after the end of infusion at the Weeks 2, 6, 12, 20. An additional PK sample will be collected at Week 24 End of Study/Early Termination Visits.
18. Serum samples for measurement of sUA levels will be collected at the Screening Visit, the Week -4 Visit and the Week -2 Visit during the Run-in Period; within 48 hours prior to each pegloticase infusion and after the end of each pegloticase infusion prior to discharge from the site during the Pegloticase + MTX Period on Day 1, at the Weeks 2, 6, 10, 12, 14, 20 and 22; within 48 hours prior to each pegloticase infusion at Weeks 4, 8, 16, 18. Additional serum samples for sUA levels will be collected at non-infusion Visits at the End of Pegloticase Infusions Visit (if applicable) and the Week 24/End of study/Early Termination Visit and 3-

month Follow-up Visit. A subject with sUA level  $>6$  mg/dL (based on the local or central laboratory) at 2 consecutive study visits, beginning with the Week 2 Visit, will be discontinued from pegloticase treatment and remain on study. If a subject's previous visit pre-infusion sUA was  $<6$  mg/dL – sUA result is not required for the following infusion visit (local pre-infusion sUA may be drawn at the same time as central pre-infusion sample). If a subject's previous visit pre-infusion sUA was  $>6$  mg/dL – local sUA is required to be resulted (within 48 hours) to confirm stopping criteria was not met. See Section 9.6.2.1 and the Laboratory Manual for instructions for alternate scenarios. In the event of an AE suspected to be an IR, a serum sample will be collected at that time or at the subsequent visit for evaluation of pegloticase antibodies.

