### **9.3 sUA Discontinuation Criteria**

Individual Subject sUA Discontinuation Criteria: Subjects with a pre-infusion sUA level  $>6$  mg/dL at 2 consecutive study visits beginning with the Week 2 Visit will discontinue treatment and remain in the study for Follow-Up visits only, including the 30-day Follow-up Email/Phone call, Week 24/End of Study/Early Termination and 3 Month Post-Treatment Follow-up Visits.

Note: The sUA Discontinuation Criteria only pertain to individual subjects and are not sUA Discontinuation Criteria for a group or specific infusion duration.

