### **9.4.3 Removal of Subjects from Therapy or Study**

Every effort should be made to retain a subject in the study to monitor their safety for at least 3-months of follow-up. Subjects who are removed from pegloticase therapy should remain on study for Follow-Up visits only, including the 30-day Follow-up Email/Phone call, Week 24/End of Study/Early Termination and 3 Month Post-Treatment Follow-up Visits barring withdrawal of consent for study participation. However, subjects may withdraw consent or discontinue participation from the study at any time, without prejudice to further treatment. In addition, the Investigator may discontinue a subject from treatment at any time. The primary reason for discontinuation from the study and/or study drug should be recorded on the eCRF.

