## 3.2 Handling of Missing Data

Aside from responder rates, where non-responder imputation is planned (see Exploratory Endpoints, [Section 3.4.3](#)), summary statistics will be computed for each efficacy endpoint using the Observed Cases (OC) with no imputation for missing data.

Unless otherwise specified, no other imputation of missing values will be done.

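### The Month 6 proportion-of-time summary normally drops subjects whose last infusion is at Week 16 or earlier, so it is selected toward subjects still on treatment and biased upward

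*SAP*

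**What the plan says.** SAP 3.4.2.1 defines the proportion of Month 6 time with sUA below 6 mg/dL. It uses this proportion to classify responders and also summarises it descriptively. For the descriptive summary, a subject with at most one "data point in the period, then the proportion of time will not be calculated". Off-treatment values are wanted: "Results from visits where an infusion was not performed (e.g. subject discontinued pegloticase but remained in study) will be used when available". SAP 3.2 says that, apart from responder rates, "summary statistics will be computed for each efficacy endpoint using the Observed Cases (OC) with no imputation for missing data".

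The same section treats these subjects differently for the responder endpoint. A subject who met the sUA discontinuation criterion, or who has sUA from fewer than two Month 6 visits, is a non-responder and stays in the denominator.

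SAP 3.4 expects data to be collected through planned study completion after treatment is stopped. It says that, in general, "treatment policy strategy will be used to account for the ICEs for defining estimands corresponding to continuous efficacy endpoints".

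The protocol plans less than that. Section 9.4.3 says "Subjects who are removed from pegloticase therapy should remain on study for Follow-Up visits only", and lists the 30-day contact, Week 24 and the 3-month visit. Section 9.3 repeats this for subjects stopped by the sUA rule, who "remain in the study for Follow-Up visits only". Section 9.4.3.1.1 adds the End of Pegloticase Infusions Visit. The sUA footnote to the Schedule of Assessments agrees: "Additional serum samples for sUA levels will be collected at non-infusion Visits at the End of Pegloticase Infusions Visit", at Week 24 and at the 3-month visit.

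**The concern.** Whether a subject enters the summary depends on the outcome being summarised. Losing urate control at two consecutive visits stops treatment. Stopping treatment removes the Week 20 and Week 22 visits, and without them there is normally a single Month 6 value and no calculated proportion. The summary therefore tends to lose the subjects with the worst urate control.

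Two results in one SAP section would then rest on different denominators. The responder rate keeps these subjects as failures, and the mean proportion of time leaves them out. A reader who takes the mean as the cohort's urate control would be misled. The planned count of subjects missing all Month 6 data does not identify this group, because each of them has one value.

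**Working it through.** The plan gives no figure for this summary, so there is none to reproduce. Its only design calculation concerns infusion reactions and supplies just the cohort size used here, 110.

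**Step 1: planned Month 6 sUA by last infusion.** Inputs:
- SAP Table 1 windows for sUA: Week 20 = days 135–148, Week 22 = days 149–162, Week 24 = day 163 or later.
- End of Pegloticase Infusions Visit about 2 weeks after the last infusion (Protocol, Duration of Treatment and Follow-up).
- Infusion day = 1 + 7 × week. The visit day is taken as infusion day + 14.

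Results:
- Last infusion at Week 16: day 113 + 14 = 127, before day 135. Adding 3 days' slack to both the infusion and the visit gives 116 + 14 + 3 = 133, still short. Only Week 24 remains, as it does for every earlier stop.
- Last infusion at Week 18: day 127 + 14 = 141, inside Week 20. With Week 24 this makes two values. If the visit takes place within 7 days (127 + 7 = 134), it misses the window and one value remains.
- Last infusion at Week 20: the Week 20 value, day 141 + 14 = 155 (Week 22) and Week 24 make three values.

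So 9 of the 11 possible early-stop times (Day 1 to Week 16) leave one planned Month 6 value. For the sUA rule, meeting it at Weeks 4 to 18 (8 of 10 possible visits) leaves one value, and meeting it at Week 20 or 22 leaves two or more. These are shares of stop times, not of subjects.

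Footnote 4 of the Schedule speaks of scheduled visits during off-treatment observation, but it refers to 9.4.3 for them, so it adds none.

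**Step 2: samples that could add a point.** Unscheduled sUA counts (SAP 3.1.7). The documents do not say whether a 3-month sample that falls inside Month 6 counts. If it is taken at +91 days and counted, last infusions at Week 8 (57 + 91 = 148) and Week 10 (71 + 91 = 162) gain a second value, and 7 of 11 stop times remain excluded.

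**Step 3: illustrative size.** All inputs except n = 110 are assumptions. A fraction f stops early, and a share s of these has one value. The mean proportion of time is m = 0.95 on treatment, 0.30 in late stoppers, and 0 in excluded subjects.
- Excluded fraction: e = f × s
- Mean with everyone kept: A = (1 − f) × m + (f − e) × 0.30
- Reported mean: R = A / (1 − e)

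For f = 0.30 and s = 9/11: e = 0.245, A = 0.70 × 0.95 + 0.055 × 0.30 = 0.681, R = 0.681 / 0.755 = 0.903.

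| f | s | Excluded of 110 | R | A |
|---|---|---|---|---|
| 0.15 | 9/11 | 13.5 | 0.930 | 0.816 |
| 0.30 | 9/11 | 27.0 | 0.903 | 0.681 |
| 0.45 | 9/11 | 40.5 | 0.866 | 0.547 |
| 0.15 | 7/11 | 10.5 | 0.911 | 0.824 |
| 0.30 | 7/11 | 21.0 | 0.862 | 0.698 |
| 0.45 | 7/11 | 31.5 | 0.801 | 0.572 |

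With m = 0.90 and s = 9/11, R is 0.881, 0.857 and 0.822, against A of 0.773, 0.646 and 0.520.

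The Phase 3 response rate of 42% (Protocol 7.2) is not used to anchor f. It is a response rate at Months 3 and 6 without methotrexate, not a stopping rate.

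**The case against.** The strongest reply is that this is not an endpoint. The listed secondary endpoints are the responder proportion, the composite event proportion and the time to that event. The responder analysis already counts these subjects as failures. The SAP also reports how many met the sUA criterion and how many stopped under the stopping rule. All of that stands, and it limits the importance of the point.

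Second, exclusions are partly visible. SAP 3.1.1 requires continuous summaries to show the number of subjects and every table to show the analysis-set size, so the difference gives the number left out. That also stands, but the difference does not say why they are missing.

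Third, one value cannot be interpolated, so the rule follows from what can be computed. Scoring every stopper as 0% would invent data: a subject who stopped for an adverse event may have a Week 24 sUA below 6 mg/dL. This is a sound reason to limit any 0% score to subjects who met the sUA criterion.

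Fourth, a reader might infer three stronger things that the documents do not support:
- That nearly everyone who stops is excluded. This depends on a stopping distribution that is not given, and late stops and extra samples keep some subjects in.
- That the summary covers only responders and will be near 100% whatever the failure rate. On-treatment subjects with isolated high values, and subjects who meet the rule at Week 20 or 22, are included. In the table the reported mean falls as stopping rises.
- That the SAP declares this summary to be treatment policy. The statement in 3.4 is general, the summary has no estimand of its own, and 3.2 points to observed cases. Some exploratory endpoints are redacted, so the general statement may be aimed at analyses that cannot be seen.

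**Conclusion.** The concern holds in a limited form. The exclusion rule and the post-treatment visit plan together leave subjects with a last infusion at Week 16 or earlier normally outside this summary. It is then selected toward subjects still on treatment and biased upward. It also sits awkwardly beside the general treatment-policy statement, because no sUA is planned at Weeks 20 and 22 after stopping.

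Under the main assumptions (15% to 45% stop early, 9/11 of them with one value), the reported mean is about 0.93 to 0.87, against 0.82 to 0.55 with excluded subjects at 0. The gap is about 0.11 to 0.32. If 3-month samples count (7/11), it is about 0.09 to 0.23. Because some excluded subjects may have spent time below 6 mg/dL, scoring them all at 0 gives the largest gap under each set of assumptions. Not every excluded subject is a urate failure, since Protocol 9.4.3.1 lists other reasons for stopping.

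No listed endpoint changes, including the secondary responder endpoint. This is an inexpensive improvement to a descriptive figure, not a fault in the trial's main conclusions.

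**What to change.** In SAP 3.4.2.1:
1. Label the existing summary as observed cases. Footnote the number excluded for having at most one Month 6 data point, split into subjects who met the sUA discontinuation criterion and subjects who stopped or lack data for other reasons.
2. Add a composite version that assigns 0% of Month 6 time to every subject who met the sUA discontinuation criterion, in line with the existing non-responder rule. Do not assign 0% to subjects who stopped for other reasons. Those with at most one value stay uncalculated and are counted in the footnote.

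In SAP 3.4, state that the general treatment-policy strategy does not apply to this summary.

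The composite mean will depend on why subjects stop. If none of the early stoppers met the criterion, it equals the observed-case mean. If all of them did, it is (1 − f) × 0.95 under the assumption above: 0.81, 0.67 and 0.52 for f = 0.15, 0.30 and 0.45.

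The cost is some SAP wording, one extra derivation and a less favourable mean beside the current one. No new data are needed.
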